Full Study Protocol

GENERAL INFORMATION

Lottery Incentive Nudges to Increase Influenza Vaccinations

[name].

[contact]

June 28, 2021

IRB#: 2021-0484

BACKGROUND AND OBJECTIVES

On average, 8% of the US population gets sick from flu each flu season (Tokars et al., 2018). Since 2010, the annual disease burden of influenza has included 9-45 million illnesses, 140,000-810,000 hospitalizations, and 12,000-61,000 deaths (CDC 2020). The CDC recommends flu vaccination to everyone aged 6+ months, with rare exception; almost anyone can benefit from the vaccine, which can reduce illnesses, missed work, hospitalizations, and death (CDC 2019). In light of the poor health outcomes for patients and substantial costs realized by healthcare systems in treating flu and related complications, it is important to improve vaccination.

Successful efforts to motivate patients to get vaccinated have included text message reminders (Milkman et al., 2021) and financial incentives (Lau et al., 2012), including a lottery for grocery gift certificates (Moran et al., 1996). This suggests that a lottery or raffle approach could be a worthwhile investment for healthcare systems, given the presumed emotional appeal of a very large reward and the anticipated savings in resource utilization costs of getting patients vaccinated. For example, Prospect Theory (Kahneman & Tversky, 1979) posits that people tend to overweight very low probabilities, which can enhance the relative salience of high payoffs in state lottery tickets with a type of "possibility effect" that is more pronounced as you approach 0% likelihood with the same expected value (EV). However, high-stakes, low-probability lottery incentives and direct payments have not yet been attempted in the domain of immunizations. Within healthcare, research on high-stakes lotteries as an incentive appears limited to efforts to encourage survey responses—arguably not a behavior that personally benefits or affects participants in the same way as flu shots—and to examine this among clinicians, who are arguably accustomed to high compensation in a way that the average patient is not (Halpern et al., 2011).

With the current study, we hypothesize that, among incentives of equal perceived EV or equal implementation costs, people are more likely to get vaccinated in response to lotteries with very high payoffs than to small certain cash payout or slightly higher-probability, more moderate payoffs. In particular, given the potential appeal of official state lottery tickets, we will include the promise of Pennsylvania scratch-off lottery tickets among our study arms. We further

hypothesize that lotteries will outperform simple reminders (encouraging respondents to get the flu shot at their upcoming appointment) and the standard of care, representing the ambient healthcare system and public health campaigns to increase vaccination.

Our specific aims are:

- 1. Evaluate whether providing any monetary incentive has a larger effect on vaccination rates than simple reminders or no message.
- 2. Evaluate whether lotteries are more effective than an equivalent-cost, certain \$1 cash payout.
- 3. Subject to available sample, evaluate which variations in prize-probability combinations and their presentation are most effective, allowing us to model the curvature of the prize-probability frontier.

PROCEDURES

Research Design

Patients at Geisinger who have a primary or specialty care appointment scheduled during the study period will be randomly assigned to a study arm. Outcomes during the 2021-2022 flu season will be compared between study arms.

Study Population

There are 2 separate populations to consider in the current study: the primary target population that will be randomized into an experimental condition and potentially contacted, and the household members of the primary population, who will not experience an intervention and will only be included for data analysis purposes.

1) Primary target population

Inclusion Criteria:

- Aged 18 or older
- Geisinger primary care provider (PCP) assigned
- Upcoming appointment with PCP or select specialist who stocks and can administer the vaccine during the study period

Exclusion Criteria:

- Has contraindications for flu vaccination
- Note: we will respect opt-out communication preferences, but will include patients in the study if they haven't opted out of at least one communication modality employed

2) Secondary population (data analysis only): Household members

Inclusion Criteria:

- Household members of primary target population
- Current Geisinger patient

Recruitment and Enrollment. All patients will be recruited and enrolled from Geisinger; MIT/NBER will not be involved in recruitment or enrollment. Patients meeting the primary target population criteria will be enrolled into one of 4-9 experimental conditions. Anticipated enrollment number for this primary target population is at least 39,224. Only patients from this primary target population will be contacted. However, health record data will be accessed to assess secondary outcomes for household members of this target population (expected N of 80,000). This brings the total planned enrollment to 119,224 participants.

Detailed Study Procedures.

Eligible subjects, as described above and in 2.2 Eligibility Criteria and 2.3 Age Limits, will be randomized into one of the intervention arms described below. At a minimum, assuming n=39,224, subjects will be randomized among four arms:

#1: Pennsylvania Lottery Scratch-Off. PA Lottery \$1 scratch-off ticket, with prizes including \$5,000 (e.g., 1-in-500,000 chance). Odds of specific prizes will not be presented in the text, to mimic their absence on the actual ticket.
#2: Certain Cash Payout. \$1 cash incentive.

#3: Reminder / Active Control Arm. Reminder message with no financial incentive. #4: No Treatment Control Arm. No additional contact beyond standard Geisinger flu shot communications.

In August 2021, we will reevaluate the number of primary care and specialty appointments scheduled for the study period. If the projected number of appointments is sufficiently high and funding suffices, we may add up to five additional arms:

#5: Additional Reminder / Active Control Arm. Reminder message with no financial incentive that uses "Reserved for you" messaging, which was the most effective messaging in our prior study (**IRB Protocol #2021-0184**).

#6: High-Payoff Raffle Absent Upfront Odds. Entry to win \$5,000. Odds will not be presented, to help equate perceptions between this raffle and Arm #1.

#7: High-Payoff Raffle with Odds (Expected Value = 1). Entry to win 5,000 (1-in-5,000 chance).

#8: Low-Payoff Raffle with Odds (EV = \$1). Entry to win \$50 (1-in-50 chance). #9: Moderate-Payoff Raffle with Odds (EV = \$1). Entry to win \$500 (1-in-500 chance).

Based on our power calculation, we need at least 9,806 patients in each arm of the study. Therefore, for each additional 9,806 patients beyond our minimum projected sample size of 39,224, we will add an additional arm.

If our sample is sufficiently high to run any of Arms 6-9, we will obtain a Small Games of Chance (SGOC) license, and we have already initiated this process in anticipation of running these arms.

Because this intervention is timed to the 2021-22 flu season, the intervention period will begin ~9/1/21. In the active conditions, participants will receive SMS text messages, phone, and/or letter reminding them of their upcoming appointment (3 days prior to the appointment, and again 1 day prior to the appointment) and telling them to ask for their flu shot. In the incentive conditions, to comply with state and federal regulations, participants will be told of a possible "cash bonus" and that they must reply to learn more about the incentive details. Participants will be informed that receipt of incentives is contingent upon documented vaccination in the electronic health record. We will also obtain data on cohabitants of the experimental subjects (anticipated n=80,000).

The primary outcome will be whether the patient was vaccinated at the scheduled appointment, as recorded in the EHR. A secondary outcome will be flu vaccination within 7 days of receiving the intervention. Additional secondary outcomes will include pre-commitment via "Y" response to the initial text, vaccination during the subsequent flu season (to assess if behavior is maintained absent subsequent incentives); rates of flu diagnoses (both using the most rigorous biological tests, "high confidence flu", and using broader criteria that also include diagnosis codes and treatment information, "likely flu"), rates of flu complications and other relevant healthcare utilization outcomes such as emergency department visits, hospitalizations, and insurance claims (for an expected ~40% of participants who are members of Geisinger Health Plan). We will also measure rates of flu vaccination, diagnoses, and complications by non-targeted household members who are likely to include older parents of patients and their spouses/partners. Finally, we will measure rates of COVID-19 vaccination in target participants and their household members.

Data Sources

In order to identify patients in the primary target population, **Business Intelligence & Advanced Analytics** (BIAA), working with **Geisinger's Phenomics and Clinical Data Core** (PACDC), will provide a list of patients (including patient identifiers such as Medical Record Number) that meet our eligibility criteria.

We will also obtain contact information (address, phone number, email address) to message participants in the primary target population from BIAA & PACDC.

After the intervention is complete, we will obtain outcomes data for both target and household population groups from BIAA & PACDC. This will include data on patient flu vaccination, diagnosis of flu, diagnosis of flu-like symptoms, presence of flu-associated complications, hospital visits, emergency department visits, and COVID-19 vaccination status. This data set will additionally include patient characteristics that will be useful as analysis covariates, such as: age, patient primary care provider, and flu-related behavior and outcomes during previous flu seasons.

STUDY DATA DETAILS

Data Management Procedures and Confidentiality. All data will be electronic. Datasets with full identifying information will only be stored on Geisinger-managed, password-protected computers of the data brokers ([name] and [name]) for the purpose of linking datasets from different sources.

A limited data set containing dates of service and ZIP codes will be shared with any non-Geisinger collaborators (e.g., Additional Principal Investigator [name] and his team) under a Data Use Agreement (pending approval) in compliance with HIPAA's Privacy Rule, and using data security protocols reviewed and approved by the Geisinger Security Office, Privacy Office, and Information Technology department.

After all data have been linked in a de-identified, coded file and analyzed, the datasets with identifiable information and any codes needed to link the identifiable information will be deleted. After the de-identified data have been fully analyzed, the de-identified dataset will be shared along with publications from this study. The deidentified data will not be destroyed or removed after any prespecified period of time has elapsed. We intend to permanently and securely archive the deidentified dataset at a research repository such as Open Science Framework (OSF) in order to be consistent with the best practices for open and reproducible science, as well as our obligation to the public as NIA-funded researchers.

The only study team members who will have access to fully identifiable and protected health information will be [name] and [name]. Non-Geisinger collaborators will have access to a limited data set containing dates of service and ZIP codes. The remaining investigators will have access to the de-identified, coded data during data analysis.

All data analysis will be conducted by [name], [name] and our non-Geisinger Collaborators. We will analyze the data using standard behavioral research analysis methods, including computing bivariate correlations, using generalized linear models, using nonparametric models for non-normally distributed data, and entering variables as independent predictors in regression models to attempt to predict desired outcomes.

RESEARCH ACTIVITIES AT OTHER SITES

Gesinger is the lead research team for this multi-site, single IRB study. Massachusetts Institute of Technology (MIT) and National Bureau of Economic Research (NBER) will cede to Geisinger's IRB. Research activities conducted at MIT and NBER will be limited to data analysis, using limited data and de-identified data, as described above. MIT and NBER will not be involved in study recruitment/enrollment or intervention administration.

BIBLIOGRAPHY

Centers for Disease Control and Prevention. (2019). Who Needs a Flu Vaccine and When. https://www.cdc.gov/flu/prevent/vaccinations.htm (Oct 11).

Centers for Disease Control and Prevention. (2020). Disease Burden of Influenza. https://www.cdc.gov/flu/ about/burden/index.html (Jan 10).

. (2019). Who Needs a Flu Vaccine and When. https://www.cdc.gov/flu/prevent/vaccinations.htm (Oct 11).

## Statistical Analysis Plan

### Brief Summary

In the current study, the study team will explore whether small incentives are effective at promoting flu vaccine uptake. The study is designed to assess whether people are more likely to get vaccinated when sent a message offering a \$1 Pennsylvania scratch-off lottery ticket, a message offering \$1 in cash, an active control message with no incentive, or no message (standard of care). A primary hypothesis is that the scratch-off messages will outperform the \$1 cash messages, active control messages (encouraging respondents to get the flu shot at their upcoming appointment) and the standard of care, representing the ambient healthcare system and public health campaigns to increase vaccination.

### Power analysis

The study team planned to enroll at least 9,806 patients per study arm. Assuming a baseline vaccination rate of 50%, this sample would allow 80% power to detect a 2% absolute percentage-point difference, or a 4% relative difference, between any two groups.

In August, 2021, we completed an analysis of the anticipated number of eligible patients in the study. This analysis suggested that our sample would be large enough to run four study arms (i.e., we projected that we would enroll more than 39,224 participants, but fewer than 49,030, the number that would have been required to add a fifth arm). Therefore, we proceeded with running only the priority four pre-registered study arms, and we anticipate enrolling a total of at least 39,224 patients across those four groups.

### Sample and Randomization

The sample includes patients who have an upcoming primary or specialty appointment where they can get a flu shot, and who, according to Geisinger's records, have not yet received a flu shot in the 2021–22 flu season. Patients are also age 18 or older, are not contraindicated for flu shots, and have an assigned Geisinger PCP. All patients are also eligible to receive text messages from Geisinger.

The four study groups include:

1. Pennsylvania (PA) Lottery Scratch-Off Financial Incentive - Participants in this arm receive a message stating that they will receive a PA lottery \$1 scratch-off ticket if they get a flu shot at an upcoming appointment. The message will mention that they could win \$5,000 (the top prize for the scratch-off game).
2. Certain Cash Payout Financial Incentive - Participants in this arm receive a message stating that they will receive \$1 in cash if they get a flu shot at an upcoming appointment.
3. Reminder / Active Control (No Financial Incentive) - Participants in this arm receive a message stating that they can get a flu shot at an upcoming appointment. These participants will not be offered a financial incentive for getting a flu shot.
4. No Intervention: No Treatment Control - No additional contact beyond standard Geisinger flu shot communications

Each day, the study team receives a list of eligible patients with flu-shot-eligible appointments in the upcoming 3 days. Patients with appointments in 3 days are randomized into the 4 groups described above. Those in groups 1-3 receive their first messages 3 days prior to their appointment.

All patients who are sent 3-day messages are sent 1-day messages, as long as they appear on the list of eligible patients the day prior to their appointment. There are two reasons patients may not appear in that list: 1) their appointment is rescheduled and they no longer have a flu-shot-eligible appointment scheduled on that date, or 2) Geisinger records are updated indicating the patient got a flu shot after randomization but before the 1-day reminder list is created, rendering the patient ineligible for a flu shot at their appointment.

In cases where a patient cancels their appointment or reschedules it for a different day, they are not sent a 1-day message.

In cases where a patient reschedules their appointment to a different time on the same day, or where the patient has a different flu-shot-eligible appointment on the same day, the patient is still sent a 1-day reminder message.

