### **Planned Analyses**

#### ***Primary Outcome***

Flu vaccination at appointment [ Time Frame: 3 days after patient is randomized ]

**Question 1:** Can lottery incentives increase flu vaccination rates better than equivalent-value cash payouts, active control messages, or no messages?

*Analysis 1a (Confirmatory):* We will test the hypothesis that patients who are sent messages with promise of an official state lottery ticket if they get vaccinated (patients randomized to message group 1) will exhibit improved flu vaccination rates compared with patients who are sent messages offering a certain \$1 cash payout if they get vaccinated (group 2).

*Analysis 1b (Confirmatory):* We will test the hypothesis that patients who are sent messages with promise of an official state lottery ticket if they get vaccinated (patients randomized to message group 1) will exhibit improved flu vaccination rates compared with patients who are sent active control messages (group 3).

*Analysis 1c (Confirmatory):* We will test the hypothesis that patients who are sent messages with promise of an official state lottery ticket if they get vaccinated (patients randomized to message group 1) will exhibit improved flu vaccination rates compared with patients who are sent no messages (group 4).

For analyses 1a through 1c, we will run an OLS regression, with a dummy variable coding for no message (group 4), active control message (group 3), cash (group 2), or state lottery (group 1).

**Question 2:** Do active control messages encouraging flu shots at an upcoming appointment increase flu vaccination rates?

*Analysis 2 (Confirmatory):* We hypothesize that patients who are sent active control messages encouraging them to get a flu shot without any associated incentives (group 3) will be more likely to get vaccinated than those in the no-contact control group (group 4). To assess this hypothesis, we will employ OLS regression with a categorical predictor variable coding for group (group 3 vs. group 4).

**Question 3:** Do small cash incentives increase flu vaccination more than active control messages or no messages?

*Analysis 3a (Exploratory):* We will test whether patients sent text messages promising small cash incentives in exchange for vaccination (group 2) are more likely to get vaccinated than those who are sent active control messages (group 3).

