*Analysis 3b (Exploratory):* We will test whether patients sent text messages promising small cash incentives in exchange for vaccination (group 2) are more likely to get vaccinated than those who are not sent any messages (group 4).

For Analyses 3a and 3b, we will run one OLS regression, with a dummy variable coding for no message (group 4), simple message (group 3), or cash (group 2).

We will not correct for multiple comparisons in the analyses above, as adjustment is not appropriate for individual testing, where each result must be statistically significant to reject its associated

individual null hypothesis (Rubin, 2021). That is, each significant result is an indicator of a specific null hypothesis rejection and has no direct bearing on the success of other hypotheses or the overall study.

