### **Secondary outcomes**

We will use the approaches described in analyses 1-3 above to evaluate the impact of the intervention on the secondary outcome measures listed in the pre-registration:

1. Flu vaccination within 7 days [ Time Frame: Within 7 days of when patient is randomized ]

Received flu vaccination

2. Flu diagnosis [ Time Frame: During the 2021-22 flu season (Up to 8 months, from the time the patient is randomized through April 30, 2022) ]

Received a "high confidence flu" diagnosis (with positive polymerase chain reaction [PCR]/antigen/molecular test) and/or "likely flu" diagnosis (as assessed via International Classification of Disease [ICD] codes or Tamiflu administration or positive PCR/antigen/molecular test)

Note that "likely flu" is a superset of the "high confidence flu" diagnoses.

3. Flu complications [ Time Frame: During the 2021-22 flu season (Up to 11 months, from the time the patient is randomized through July 31, 2022) ]

Diagnosed with flu-related complications

4. Flu vaccination (among subject cohabitants) within 28 days [ Time Frame: Within 28 days of when the study subject is randomized ]

Cohabitant of study subject received flu vaccination

This analysis will exclude patients who are both cohabitants of a subject and subject themselves

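### Patients are randomized from daily lists, but no arm comparison includes randomization date; the cost is modest precision, not bias

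*SAP*

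**What the plan says.** SAP, Sample and Randomization, describes a rolling process: "Each day, the study team receives a list of eligible patients with flu-shot-eligible appointments in the upcoming 3 days", and then "Patients with appointments in 3 days are randomized into the 4 groups described above". Only patients with no recorded flu shot this season are eligible. The protocol (Detailed Study Procedures) puts the start at about September 1, 2021. The SAP gives December 31, 2021 as the primary completion date, but no last randomization date. The text available states neither an allocation ratio nor whether assignment was simple, blocked or stratified by day.

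The primary model contains arm indicators only: "For analyses 1a through 1c, we will run an OLS regression, with a dummy variable coding for no message (group 4", with the rest of that sentence listing the other three groups. Analyses 2 and 3 have the same form. In Sensitivity analyses and robustness checks, the shared-address, logistic and messages-received checks rerun those models, and the one covariate-adjusted check adds sex, binned age and their interaction. Secondary outcomes reuse the approach of analyses 1 to 3. For flu diagnosis the window runs "from the time the patient is randomized through April 30, 2022"; for complications it ends on July 31, 2022.

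Project status says that the primary outcome has been analysed and that no secondary outcome has yet been extracted.

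**The concern.** Date is likely to predict the outcome. The eligible pool loses people as they are vaccinated, and the SAP itself notes (Previous year flu vaccination) that some patients get a shot every year regardless, so the patients left in December may differ from those in September. For diagnosis and complications, date also fixes the length of follow-up. A baseline variable that predicts the outcome, is already on file and marks the batch in which patients were assigned is an obvious adjustment term. Leaving it out keeps date-related variance in the error term, so intervals are a little wider than they need be.

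**Working it through.** **The plan's own figure.** Inputs from SAP, Power analysis: "Assuming a baseline vaccination rate of 50%, this sample would allow 80% power to detect a 2% absolute percentage-point difference" and "The study team planned to enroll at least 9,806 patients per study arm". Alpha is not stated; two-sided 0.05 is assumed. With p1 = 0.50, p2 = 0.52 and mean 0.51:

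n = [1.960 × √(2 × 0.51 × 0.49) + 0.842 × √(0.2500 + 0.2496)]² / 0.02² = (1.3856 + 0.5949)² / 0.0004 = 9,806 per arm.

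This matches exactly, and 4 × 9,806 = 39,224.

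**Precision from date adjustment.** The documents give no vaccination rate by date, so the swing w is an assumption. If uptake moves linearly by w in total around 50%, the between-day variance is w²/12 and date explains R² = (w²/12) / 0.25. The unadjusted standard error of a pairwise difference is √(2 × 0.25 / 9,806) = 0.714 points. The adjusted one is 0.714 × √(1 − R²). Power is Φ(2 / SE − 1.960). Allocation is taken as simple and equal.

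| Swing w | R² | SE, points | Power | n per arm giving the unadjusted SE |
|---|---|---|---|---|
| none | 0 | 0.714 | 80.0% | 9,806 |
| 10 points | 0.3% | 0.713 | 80.1% | 9,773 |
| 20 points | 1.3% | 0.709 | 80.5% | 9,675 |
| 30 points | 3.0% | 0.703 | 81.2% | 9,512 |
| 40 points | 5.3% | 0.695 | 82.1% | 9,283 |

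**Validity of the unadjusted model.** If each patient has the same chance of each arm on every day, assignment is independent of date. The difference is then unbiased, and its 0.714-point standard error already contains chance imbalance by day. That component has SD √(2 × (w²/12) / 9,806): 0.08 points for w = 20 and 0.16 for w = 40. A simulation (85 enrolment days assumed, simple equal allocation, 1,500 runs) gave type I error of 5.2% (w = 20) and 5.8% (w = 40) unadjusted, against 5.6% and 6.0% with day effects. The Monte Carlo error is about 0.6 points, so there is no sign that the unadjusted test fails.

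**If arms were balanced within daily lists.** The estimate already has the smaller standard error, but the unadjusted model reports 0.714. For w = 40 the reported value is too wide by 0.714 / 0.695 = 1.028, about 3%.

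**Uncommon outcomes.** No event rates are given. As an illustration, a diagnosis risk falling linearly from 8% to 4% gives R² = (0.04² / 12) / (0.06 × 0.94) = 0.24%. A fall from 8% to zero gives (0.08² / 12) / (0.04 × 0.96) = 1.4%.

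**Follow-up.** From September 1 to April 30 is 241 days. From December 28 it is 123 days (an assumed last date: December 31 less the 3-day primary window). To July 31 the figures are 333 and 215.

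**Degrees of freedom.** 85 to 122 day indicators among 39,224 patients use 0.2% to 0.3%.

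**The case against.** The strongest reply is that unadjusted OLS on arm indicators is valid for a randomized comparison, that the gain is small and rests on swings the documents do not report, and that several robustness checks are already planned. The power figures are also for vaccination near 50%, while the main change falls on the secondary outcomes, two of which are probably much rarer. Day effects in a logistic model of a rare outcome would produce days with no events, and they change the odds ratio to a conditional one.

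Most of this stands and limits the point. It does not remove it: the date is needed anyway to apply the 3-, 7- and 28-day windows, the term costs almost nothing in OLS, and for the secondary outcomes it can still be fixed before data are seen. Two of the four secondary outcomes are themselves vaccination outcomes, for which the tabulated gains are a closer guide.

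A reader might infer three stronger things.

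- **Day-level imbalance biases the arm comparison.** It does so only if allocation shares changed with date. If one arm's share drifted from 27.5% to 22.5% while uptake fell 20 points, the bias would be about (0.05 × 0.20 / 12) / 0.25 = 0.33 points; from 30% to 20% it would be about 0.67. The documents give no sign of such drift.
- **Unequal follow-up biases the diagnosis and complication comparisons.** Under randomization with constant allocation, the mix of follow-up lengths has the same distribution in every arm.
- **Day is a design stratum that the analysis must respect.** Lists are daily, but no blocking or stratification by day is described.

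**Conclusion.** The point holds as a minor efficiency recommendation. No planned arm comparison uses randomization date, and including it would bring a small gain: about 0.1, 0.5 or 2 percentage points of power for assumed uptake swings of 10, 20 or 40 points, and probably less for flu diagnosis and complications. These figures assume a linear trend, a mean of 50%, equal simple allocation, two-sided alpha 0.05 and 9,806 per arm. The enrolment period of about September 1 to late December is inferred. Under a constant allocation ratio neither the estimates nor their standard errors are invalid; if lists were balanced by day, the error is on the conservative side. Nothing here threatens the trial's conclusions.

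**What to change.** 1. Before extracting the secondary outcomes, prespecify randomization-date effects (calendar day, or week where days are sparse) in their OLS models. For cohabitant vaccination, use the linked subject's randomization date.
2. In the logistic checks use week or month terms, to avoid strata with no events.
3. Leave the analysed primary model unchanged. Add a date-adjusted version beside the sex-and-age robustness check, labelled as a post hoc sensitivity analysis.
4. State the allocation ratio and method, and report arm counts by week, so that a reader can confirm that shares did not drift.

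The cost is slightly more analysis work and a logistic check whose odds ratio is conditional on date, and so not directly comparable with the unadjusted one. No new data are needed.
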